The complement to the Evaluable population will be referred to as the Excluded population. It is worth remarking that for this study, if a patient has a history of concomitant EoE or if the esophagus looks suspicious for EoE or other condition, or if patient is symptomatic on screening dysphagia question, quantified by a score of >3 on the dysphagia question on at least 1 day during screening, then the following esophageal biopsies are collected during the baseline EGD:

- A set of 2 fragments from the distal esophagus
- A set of 2 fragments from the mid-proximal esophagus
- Up to 2 extra specimens may be collected if there are any additional areas of interest.

A count of >6 eosinophils/hpf in at least 1 esophageal site will be considered diagnostic for esophageal eosinophilia for the purposes of this study. In cases when there is a history of EoE, this could reflect active EoE although fulfillment of the diagnostic criteria for that condition may not be certain (see [Appendix 5](#) for details).

The Per Protocol (PP) population is defined as Evaluable population patients who received at least 1 infusion of study drug and did not have significant protocol violations possibly interfering with assessment of efficacy.

Statistical Analysis cont.

The Safety population is defined as all patients who are randomized and have received at least 1 infusion of study drug.

The Evaluable and Excluded populations will be used for all efficacy analysis. The Per Protocol population will be used for the primary endpoints and select secondary endpoints analyses. The Safety population will be used for all safety analysis.

Patient disposition and reason for early discontinuation will be tabulated. Patient demographics, baseline characteristics, and treatment exposure will be summarized.

Efficacy Analysis: To evaluate the clinical benefit of AK002 in adult patients with active EoD when compared with placebo, efficacy endpoints will be co-primary.

The first co-primary endpoint will be analyzed using the Fisher's exact test. Patients who experience an intercurrent event (ICE), i.e., exit the study prematurely or initiate prohibited or restricted medications, prior to the end of Week 24 will be treated as non-responders. Proportion of responders and the associated 95% confidence interval (CI) will be presented for each treatment group. The between-group difference and the associated 95% CI will also be computed and presented.

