5.1 Study Overview

This is a Phase 3, multicenter, randomized, double-blind, placebo-controlled study to evaluate the efficacy and safety of AK002 in patients with moderately to severely active EoD without EG who have an inadequate response with, lost response to, or were intolerant to standard therapies.

Patients enrolled in the study will receive 6 infusions of placebo or AK002 administered every 4 weeks and will be followed for 12 weeks after last dose unless patients elect to enter the optional open-label extension (OLE) period of the study.

Patients will be consented and then screened for 21–45 days prior to Day 1. Patients who meet all eligibility criteria can be enrolled into the study. Patients who do not meet all eligibility criteria at screening, or who qualify at screening but are not enrolled, may be assigned a new patient identification number and rescreened once. Patients rescreened within 30 days of signing the initial consent will not need to sign a new informed consent form (ICF) if no changes have been made to the ICF.

Patients will undergo EGD and colonoscopy with biopsy at screening and again 4 weeks after last dose. The EGD and colonoscopy should take place on the same day in order to minimize effects of procedure premedication on the PRO scores. For patients with a history of EoE and/or with a score of ≥ 3 on the dysphagia question on at least 1 day during screening, esophageal

biopsies will also be collected at screening and postdose. Biopsies from the gastric mucosa, duodenum, colon, and esophagus (as applicable) will be taken and reviewed by a central pathology reader. Additional biopsies will be collected for exploratory analysis.

The study is designed as follows:

- A screening period of 21–45 days with baseline evaluations for study eligibility, including active symptoms of disease (gathered by the patient reported outcome [PRO] questionnaire completed during screening) and EGD and colonoscopy (performed on the same day) with biopsy.
- Stool antigen test for *Helicobacter pylori* (*H. pylori*) will be assessed during screening to confirm no active *H. pylori* infection exists. If *H. pylori* is detected in tissue biopsies by the central pathologist, the patient should be excluded from the study.

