12.1 Screening Period

- 1) Obtain written informed consent.
- 2) Assign the participant a PID.
- 3) Begin the collection of SAE related to any screening activities.
- 4) Collect demographics and medical history.
- 5) Record prior and concomitant medications.
- 6) Determine body weight and height.
- 7) Activate patient access to the ePRO questionnaire portal and instruct patient on use of the website to complete the questionnaire(s). Use the ePRO Teaching Tool to instruct the patient on use of the electronic platform (Appendix 7).
- 8) **CCI** [REDACTED] to be completed by the patient.
- 9) Perform baseline diet assessment.
- 10) Complete previous treatments and procedure review.
- 11) Obtain vital signs before blood draws and after patient at rest ≥ 5 minutes.

- 12) Perform a complete physical examination.
- 13) Obtain a 10-lead or 12-lead ECG before blood draw.
- 14) Collect the following samples for the central laboratory:
 - a) Blood for CBC with differential
 - b) Blood for Chemistry (sample to be tested for FSH and hCG if patient is of childbearing potential)
 - c) Urinalysis
 - d) Blood for serology testing (includes *Strongyloides stercoralis*)
 - e) Blood for PK
 - f) Blood for ADA
 - g) Blood for total serum IgE
- 15) Provide patient a stool collection kit and ask patient to provide a stool sample while on site or return it to the site within 1 day of collection.
- 16) Perform a screening EGD and colonoscopy with biopsy following instructions provided by Allakos any time during the screening period. The EGD and colonoscopy should take place on the same day in order to minimize effects of procedure premedication on the PRO scores. Patient should arrive fasting for the EGD procedure as specified by instructions from the EGD provider.
- 17) **CC1** to be completed by the patient on screening Day 19 (not a clinic visit).
- 18) Using results from the central histology reader, confirm that the eosinophil count from the gastric and/or duodenal biopsies qualify the patient for the study and no exclusionary criteria are found on the EGD or colonoscopy.
- 19) Review all ePRO scores. Since the bowel preparations could artificially increase the scores, exclude ePRO scores from the day before and the day of colonoscopy when assessing eligibility criteria.

12.2 Prior to Day 1

The following procedures will be performed prior to Day 1:

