15.2 Analysis Populations

The Safety population is defined as all patients who are randomized and have received at least 1 infusion of the study drug.

The primary efficacy analysis population is the Evaluable population defined as all randomized patients who have received at least 1 infusion of the study drug and at study entry do not meet any of the following criteria:

- 1) >6 eosinophils/hpf in at least 1 esophageal biopsy at baseline.
- 2) Documented history of irritable bowel syndrome and baseline diarrhea intensity ≥ 3 .

The complement to the Evaluable population will be referred to as the Excluded population. The Per Protocol (PP) population, defined as Evaluable population patients who have received at least 1 infusion of study drug and did not have significant protocol violations possibly interfering with assessment of efficacy. The Evaluable and Excluded populations will be used for all efficacy analysis. The PP population will be used for the primary endpoints and select secondary endpoint analyses. The Safety population will be used for all safety analysis.

The study statistician along with the study team will review protocol deviations to identify patients to be excluded from the PP analysis population.

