19.5 Appendix 5: EGD and Colonoscopy Histology

Details for collecting, labeling, and shipping specimens will be provided separately in the Histology Manual.

Staining: The performance of the evaluations listed below will require the following stains for each biopsy set:

- Esophagus: 1) H&E; 2) tryptase; 3) trichrome

For patients with a history of EoE and/or with a score of ≥ 3 on the dysphagia question during screening, esophageal biopsies will also be collected at screening and postdose.

- Stomach: 1) H&E; 2) tryptase
- Duodenum: 1) H&E; 2) tryptase
- Colon: 1) H&E; 2) tryptase

Biopsies will be obtained from the following:

- **Esophagus** (if patient has a history of concomitant EoE, if esophagus looks suspicious for EoE, or if patient is symptomatic on screening dysphagia question, quantified by a score of >3 on the dysphagia question on at least 1 day during screening).

- A set of 2 fragments from the distal esophagus
- A set of 2 fragments from the mid-proximal esophagus
- Up to 2 extra specimens may be collected if there are any additional areas of interest.

A count of ≥ 15 eosinophils/hpf in at least 1 esophageal site will be considered diagnostic of EoE for the purposes of the study.

- **Stomach**

- 4 specimens from separate areas of the gastric antrum (2–5 cm proximal to the pylorus)
- 4 specimens from separate areas of the gastric corpus (2 from the proximal lesser curvature and 2 from the greater curvature)
- Up to 2 extra specimens may be collected if there are any additional areas of interest.
- 1 fragment will be collected for exploratory analysis (shipped to Allakos directly).

19.5 Appendix 5: EGD and Colonoscopy Histology cont.

- **Duodenum**
 - 4 fragments of duodenal mucosa from the second and third part of the duodenum
 - Up to 2 extra specimens may be collected if there are any additional areas of interest.
 - 1 fragment will be collected for exploratory analysis (shipped to Allakos directly).
- **Colon**
 - At least 2 fragments (preferably 3 fragments) each from terminal ileum; ascending, transverse, descending, and sigmoid colon; and rectum
 - Up to 2 extra specimens may be collected if there are any additional areas of interest.
 - 1 fragment each will be collected from terminal ileum; ascending, transverse, descending, and sigmoid colon; and rectum for exploratory analysis (shipped to Allakos directly).

The following will be reported for esophageal biopsies:

- Maximum number of eosinophils/hpf

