Appendix 7: ePRO Teaching Tool cont.

THINGS TO REMEMBER WHEN USING THE ELECTRONIC QUESTIONNAIRES

- When you first log on to ViedocME the HOME screen will display the 1st questionnaire that is due for the day, which is usually the 10-question PRO questionnaire as shown below:

- Click SEND when you have answered all 10 questions on the daily EG/EoD PRO questionnaire:

- You will daily complete one additional question each, about dysphagia (difficulty swallowing) and constipation following the completion of the 10 question ePRO questionnaire.
- On study visit days you will access ViedocME to complete the SF-36 Health Survey.
- On screening Day 19 and study days 7, 28, 225 and ET, you will complete the 1-question PGIS via ViedocME.
- On study days 7, 28, 225, and ET, you will complete the 1-question PGIC via ViedocME.

COMPLETING THE DAILY QUESTIONNAIRES DURING THE STUDY

You will complete the EG/EoD questionnaire, and the additional questions during the entire duration of the study:

- SCREENING period (BEFORE you receive 1st study drug)
- TREATMENT period (WHILE you are receiving study drug)
- FOLLOW UP period (AFTER you have received all study drug or at the last study visit)

During the screening period, the questionnaire is used to determine if your symptoms are appropriate in type and intensity to be enrolled into the study.

Patients with a history of EoE and/or with a score of ≥ 3 on the dysphagia question during screening will also have esophageal biopsies collected during the EGD at screening and postdose.

You will start completing the daily questionnaires (EG/EoD daily questionnaire, and the additional questions) on the first day of your participation in this study and will complete the questionnaires until your last day of participation in this study.

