#### 6.1.5 Primary Analysis Population

The primary efficacy analysis population is the Evaluable Population defined as all randomized subjects who have received at least 1 infusion of study drug, and at study entry do not exhibit any of the following criteria:

1.  $>6$  eosinophils per hpf in at least one esophageal biopsy at baseline
2. Documented history of irritable bowel syndrome and baseline diarrhea intensity  $\geq 3$ .

- The complement to the Evaluable population will be referred to as the Excluded population. It is worth remarking that for this study, if a subject has a history of concomitant EoE, or if

esophagus looks suspicious for EoE or other condition, or if patient is symptomatic on screening dysphagia question, quantified by a score of  $>3$  on the dysphagia question on at least 1 day during screening, then the following is undertaken:

- A set of 2 fragments is collected from the distal esophagus
- A set of 2 fragments is collected from the mid-proximal esophagus
- Up to 2 extra specimens may be collected if there are any additional areas of interest.
- A count of  $>6$  eosinophils per hpf in at least one esophageal site will be considered diagnostic of at least having esophageal eosinophilia for the purposes of the study and in cases where there is a history of EoE this could reflect active eosinophilic esophagitis although fulfillment of the diagnostic criteria for that condition may not be certain (see Appendix 5 for details).

Analysis will be conducted on the complement population, referred to as Excluded Population, and is planned as exploratory. In addition, for completeness purposes, analysis will be conducted on the mITT population to show what the study results would have been on all the subjects prior to removing those with confounding conditions outlined above.

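### The patient-facing ePRO teaching tool prints the dysphagia score that triggers esophageal biopsy, a biopsy on which one exclusion from the primary population depends

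*Protocol*

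**What the plan says.** Protocol Appendix 7 is written to the patient. In its account of the daily questionnaires it states that patients with an EoE history or a score of at least 3 "on the dysphagia question during screening will also have esophageal biopsies collected during the EGD at screening and postdose". Protocol Section 12.1, item 7, gives sites this instruction: "Use the ePRO Teaching Tool to instruct the patient on use of the electronic platform".

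The primary efficacy population is the Evaluable population: all randomized, dosed patients who meet neither of two baseline exclusions (Protocol Section 15.2; SAP Section 6.1.5). The first is more than 6 "eosinophils/hpf in at least 1 esophageal biopsy at baseline". The second is a documented IBS history together with baseline diarrhea intensity of at least 3. Neither document says how to classify a patient who had no esophageal biopsy.

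Esophageal biopsy is not done in everyone. Protocol Section 5.1 ties it to an EoE history or a score of at least 3 "on the dysphagia question on at least 1 day during screening, esophageal" biopsies being the result. Protocol Appendix 5 adds a visual trigger and, in its list of biopsy sites, a different cut-off: "if esophagus looks suspicious for EoE, or if patient is symptomatic on screening dysphagia question, quantified by a score of >3". The Statistical Analysis part of the Protocol Synopsis widens the visual trigger: "if the esophagus looks suspicious for EoE or other condition".

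**The concern.** A screening self-report with a procedural consequence is best collected from someone who does not know the threshold. Here the threshold and its consequence are handed over as scoring begins. Dysphagia is not one of the six TSS items (Protocol Section 4.1), nor one of the symptoms in inclusion criterion 5, so a low answer costs the patient nothing in eligibility, while reaching the cut-off adds biopsies at two endoscopies.

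What is at stake is membership of the population used for both co-primary endpoints. The sponsor removes patients with esophageal eosinophilia because that variable was one of eight that most influenced TSS change in AK002-016 (Protocol Section 4.5.1; SAP Section 4.2.1). If answers drift below the printed score, some such patients go unbiopsied and remain in the population the exclusion was meant to clear.

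**Working it through.** The plan states no figure on this point, so the check is mainly a comparison of passages.

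**1. Is the cut-off seen before scoring?** Yes. The tool is used at screening (Section 12.1, item 7), the questionnaire is activated on screening Day 1 (Protocol Table 2, note 10), and the tool ends by telling the patient to start the diary that day.

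**2. Does the patient need it?** No. Appendix 10 gives the 0 to 10 dysphagia item with its own instructions. The cut-off matters only to the site.

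**3. What triggers the biopsy?**

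| Place | Score | At least 1 day stated | Visual suspicion |
|---|---|---|---|
| Protocol Synopsis, Study Design | 3 or more | no | no |
| Protocol 5.1 | 3 or more | yes | no |
| Protocol 11.2.4 | 3 or more | no | no |
| Protocol Appendix 7 | 3 or more | no | no |
| Protocol Synopsis, Statistical Analysis | above 3 | yes | yes |
| SAP 6.1.5 | above 3 | yes | yes |
| Protocol Appendix 5 | both | yes, with above 3 | yes |

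Every row also lists EoE history. The item is scored in whole numbers, so the two cut-offs disagree for a patient whose highest score is exactly 3.

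**4. When does the self-report decide?**
- EoE history: biopsied whatever the score.
- No history, suspicious-looking esophagus: biopsied under the three passages that list visual suspicion, but not required by the other four.
- No history, not suspicious, score reaches the cut-off: biopsied.
- No history, not suspicious, score stays below: not biopsied. The first exclusion cannot be met, and the patient is Evaluable unless the second applies.

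The score decides between the last two. Section 12.1, item 16, allows the endoscopy at any time in screening, so only scores given before it can trigger the screening biopsy.

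**5. Could the arms differ?** Randomization follows completion of screening and is blinded and 1:1 (Protocol Section 10.2). Any misclassification is therefore balanced between arms in expectation.

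**6. Size.** The documents give no trigger rate, no misreporting rate and no rate of eosinophilia among unbiopsied patients. Dilution can be shown only by assumption. Let m be the share of Evaluable patients with undetected esophageal eosinophilia, suppose they have no TSS benefit, and keep 40 per arm and SD 12.5 (Protocol Section 15.1). The expected difference is 7.4 × (1 − m), and normal-approximation power at two-sided 0.05 is Φ(7.4(1 − m) / (12.5√(2/40)) − 1.96):
- m = 0: difference 7.40, power 75.4% (the plan states 80%; that gap is a separate matter)
- m = 5%: 7.03, 71.1%
- m = 10%: 6.66, 66.4%
- m = 20%: 5.92, 56.3%

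Here m covers every unbiopsied case, whatever the reason. The part due to the printed cut-off is unknown, so these values show how dilution scales. They do not estimate the effect of Appendix 7.

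**The case against.** The strongest reply is that misreporting is conjecture. Every patient already has an EGD and colonoscopy with at least 8 gastric, 4 duodenal and 6 × 2 = 12 ileal and colonic fragments, 24 in all before exploratory samples (Appendix 5). The esophageal set adds 2 + 2, plus up to 2 extra, so 4 to 6 fragments at the same procedure. Nothing shows that patients would shade their answers to avoid that. The tool asks them to answer as well as they can. Its sentence just before the cut-off says that the screening questionnaire determines whether symptoms suit enrollment, without saying that dysphagia does not count. A patient keen to enter might score higher, which would produce more biopsies. All of this stands: extent and direction are unknown.

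A reader might infer that patients can use the cut-off to stay in the primary analysis. The documents do not support that. The tool says nothing of the Evaluable population, the eosinophil threshold, the number of fragments or the one-day rule. Nor is a low score sufficient, because EoE history or, where listed, a suspicious appearance still leads to biopsy, and the second exclusion can still remove the patient.

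The planned mITT analysis (SAP Section 6.1.5) does not depend on biopsy status and is a partial safeguard, but it is not the primary inference. It is also fair that deleting a sentence does not cure selective biopsy itself. The consent form is not among the documents reviewed and may carry the same cut-off.

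**Conclusion.** The point holds at low severity. A patient handout discloses a threshold that patients do not need, for a self-report that in some patients decides whether the first Evaluable exclusion can be applied at all. The likely harm is modest dilution of the primary population, because several conditions must coincide: no EoE history, no visual suspicion, a score kept below the cut-off before the endoscopy, true esophageal eosinophilia, and no second exclusion.

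Two further inferences should be resisted. The result is not tilted toward AK002, since the scores are given before blinded allocation. And no number of misclassified patients should be quoted, because every input would be invented. The conclusion rests on the wording of Appendix 7 and on reading the Evaluable definition literally for unbiopsied patients.

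**What to change.** Delete the sentence with the cut-off from Appendix 7 and tell patients only that esophageal biopsies may be taken. Keep the trigger in the site-facing text (Section 11.2.4, Appendix 5 and the Histology Manual). If the consent form prints the same score, edit it in the same way. The cost is one sentence in a training handout, with no change to visits, data or sample size. It helps only patients not yet shown the tool.

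Alongside this, reconcile the seven trigger passages in step 3 so that score, number of days and visual suspicion are stated once and identically. Which trigger to adopt is for the sponsor to decide. The classification of patients without a baseline esophageal biopsy remains open after this edit and should be stated in SAP Section 6.1.5.

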Appendix 7: ePRO Teaching Tool cont.

ePRO Teaching Tool: Study AK002-021 (continued)

IT IS IMPORTANT:

- You complete AS MANY daily questionnaires as possible.
- You think about your symptoms in the same way throughout the whole study, which includes before, during and after receiving the study drug.
- You remember that each symptom should be assessed over the past 24 hours (1 day).
- You hit SEND after you have finished all questions on each questionnaire.
- You hit GO TO STARTPAGE to see if there are any additional questions that need to be answered for that day.

STUDY COORDINATORS – COMPLETE THIS UPON VIEDOCME ACTIVATION:

Questionnaire Website: <https://v4me.viedoc.net>

Username: _____

PIN (do not share with others): _____

Daily questions to answer: Use the table below to demonstrate which questions should be completed:

QUESTIONNAIRE	Screening	During Study
EG/EoD PRO questionnaire – (10) questions	X	X
Sf-36 Health Survey "Your Health and Well-Being"	X	X (ONLY DURING STUDY VISITS)
Additional Question – {1} question each	Screening	During study
Dysphagia question	X	X
Constipation question	X	X

*Additional questions for dysphagia and constipation will populate only AFTER you have completed the daily EG/EoD questionnaire.

You must hit SEND and GO TO START PAGE to see all questionnaires.

START DIARY TODAY!

Additional Information regarding diary completion on Page 4

